#### 7.5.2. Statistical Method

When the use of descriptive statistics to assess group characteristics or differences is required, the following methods will be used: for categorical variables, the number and percent of participants in each category; for continuous variables, the mean, median, standard deviation, quartiles and range (minimum, maximum).

In general all missing data will be treated as missing completely at random and no imputation will be performed except for the safety endpoints as described below. Non-analyzable data (e.g., due to major protocol violations) will be documented in the deviations.

If some safety data are available for a subject in the safety population but respective secondary endpoint related data are missing then the subject will be included in the safety analysis and data will be treated as follows for immediate AEs, solicited AEs, unsolicited AEs and SAEs.

- 1. If Severity is missing for any AE then it will be considered as an AE of maximum severity (Grade 3) "Severe" unless it's captured as SAE.
- 2. If "Relationship" is missing then it will be considered as "Related" to the vaccine administered.
- 3. If, for Start date, the day of event/condition is missing due to any adverse event then it will be imputed as the date of last dose of study vaccine.
- 4. If, for Start date, the day and month of an adverse event is missing, then it will be imputed as the date of first dose of study vaccine.
- 5. If the Stop date of an adverse event is missing then it will be treated as ongoing.

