#### 4 INVESTIGATIONAL PLAN

#### 4.1 Overall Study Design and Plan

This study is a Phase 1, single center, double blinded, randomized, controlled clinical trial to assess the safety and immunogenicity of the adjuvanted and non-adjuvanted formulation of polyvalent conjugate vaccine composed of serogroups A, C, Y, W and X *Neisseria meningitidis* capsular polysaccharides (MCV-5) as compared to the quadrivalent (ACYW) Menactra® vaccine. As this is the first clinical study with the study vaccine, the study will initially be performed in 60 adult healthy participants aged 18 to 45 years old.

The study will have 3 arms with 3 vaccines given in a 1:1:1 ratio; adjuvanted MCV-5, non-adjuvanted MCV-5 and Menactra®. Each participant will receive a single intramuscular (IM) injection of one of the three vaccines and will be followed up to six months after the vaccination. There will be 20 participants per vaccine group.

The vaccinator will be aware of group allocation, although he/she will not be able to influence or decide this allocation nor be part of the safety assessment. This will ensure that the study team, involved in assessment of safety outcomes, as well as participants, are unaware of the identity of the study vaccine

administered to them. This will help rule out bias at the time of assessment. As the reference product and study vaccines are different in appearance and composition, the vaccinator blind cannot be maintained in this study. However, the vaccinator will not be involved in the safety assessment.

In addition, immunogenicity assessments are planned to evaluate any differences in the immune responses induced by the adjuvanted and non-adjuvanted study vaccines and to compare against the reference vaccine. The study, however, is not statistically powered to determine significance of any difference. A formal sample size calculation was not performed as this is a Phase 1 trial and the first clinical study in humans with the study vaccine.

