#### All SAEs will be:

- Recorded on the appropriate SAE report form and sent to the Emmes Coordination Center within 24 hours of the site's knowledge of the event.
- Reported to the Emmes medical monitor who in turn will pass on the information to the Sponsor and SIIPL
- Reported to the site's Independent Safety Monitor
- Reviewed and followed until the event is resolved or determined to be irreversible, chronic, or stable by a study physician

SAEs will be collected on each participant for 180 days after vaccination.

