#### 6.5 Missing Data

In general, all missing data will be treated as missing completely at random and no imputation will be performed except for the safety endpoints as described below. Non-analyzable data (e.g., due to major protocol violations) will be documented in the deviations. For immunogenicity data where the antibody titer is below 1:8 (< 8), an arbitrary value of half the assay's cut-off value, 4, will be used in the analyses for those values.

If some safety data are available for a participant in the FA population, but respective secondary endpoint related data are missing, then the participant will be included in the safety analysis and data will be treated as follows for immediate AEs, unsolicited AEs and serious adverse events (SAEs).

- If Severity is missing for any AE, then it will be considered as an AE of maximum severity (Grade 3) "Severe", unless it is captured as SAE.
- If "Relationship" is missing, then it will be considered as "Related" to the vaccine administered.
- If, for Start date, the day of event/condition is missing due to any adverse event, then it will be imputed as the date of last dose of study vaccine.
- If the Stop date of an adverse event is missing, then it will be treated as ongoing.

For solicited adverse events, the following assumptions will be made:

- If dates are missing, but symptoms are reported, then the day post vaccination will be used to calculate the date of the symptom.
- If a symptom is not reported at any time through Day 7, then no imputation for missing data will be performed. The data will be summarized as not reported on the tables.

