#### 9.4.3 Unsolicited Adverse Events

The proportion of participants reporting at least one unsolicited adverse event will be summarized by MedDRA® system organ class and preferred term for each treatment group and overall. Denominators for percentages are the number of participants in the FA population. A 95% CI calculated using Clopper-Pearson methodology from a binomial distribution (SAS PROC FREQ with a binomial option) will be presented for each MedDRA® system organ class and preferred term (Table 14.3.1.7)

Unsolicited adverse events by participant will be presented in Listing 16.2.7.2.

The following summaries for unsolicited adverse events will be presented by treatment group:

- Participant level summary of maximum severity and relationship to study product by MedDRA® SOC and PT (Table 14.3.1.8.1);
- Participant level summary of related unsolicited events by maximum severity, MedDRA® SOC and PT (Table 14.3.1.8.2);

- Participant incidence of unsolicited adverse events over time by MedDRA® SOC and PT (Days 1-8, Days > 8) (Table 14.3.1.9.1);
- Participant incidence of related unsolicited adverse events over time by MedDRA® SOC and PT (Days 1-8, Days > 8) (Table 14.3.1.9.2);
- Total frequency of adverse events over time by MedDRA® SOC and PT (Days 1-8, Days > 8) (Table 14.3.1.10);
- Participant listing of non-serious adverse events of moderate or greater severity (Table 14.3.2.2);
- Bar chart of the frequency of events for non-serious adverse events by maximum severity and MedDRA® SOC (Figure 14.3.1.11);

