#### 9.5 Deaths, Serious Adverse Events and other Significant Adverse Events

A listing of deaths and SAEs (Table 14.3.2.1) will be presented including Participant ID, Adverse Event Description, number of days post dose and number of days post dose it became serious, Reason Reported as an SAE, Relationship to Treatment, Alternate Etiology if not Related, Outcome, Duration of Event (days), and whether participant discontinued due to the AE.

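### An AE with only its start day missing is dated to vaccination even when a later month is on record, so it appears under Days 1-8

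*SAP*

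**What the plan says.** SAP section 6.5 introduces its safety imputation rules with "data will be treated as follows for immediate AEs, unsolicited AEs and serious adverse events (SAEs"). The start-date rule in that list is that if "the day of event/condition is missing due to any adverse event, then it will be imputed as the date of last dose" of study vaccine. Solicited events have a separate rule based on the reported day after vaccination and are not affected.

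Protocol section 7.5.2 carries the same rule as item 3: if "the day of event/condition is missing due to any adverse event then it will be imputed as the date of last dose" of study vaccine. Item 4 then deals separately with a larger gap: if "the day and month of an adverse event is missing, then it will be imputed as the date of first dose of study vaccine". The SAP does not repeat item 4.

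On dosing, SAP section 4.1 states: "Each participant will receive a single intramuscular (IM) injection of one of the three vaccines". SAP section 3.3 defines the vaccination day as Day 1.

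The dates feed the timing summaries in SAP section 9.4.3, which are split as "SOC and PT (Days 1-8, Days > 8) (Table 14.3.1.9.1"), with the same split for related events (Table 14.3.1.9.2) and event counts (Table 14.3.1.10). SAP section 9.4.1 includes SAEs in the unsolicited summaries, and section 4.5.1.3 sets the SAE period: "SAEs will be collected on each participant for 180 days after vaccination".

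**The concern.** Because the protocol has its own item for day and month both missing, item 3 must be the rule for a known month. It replaces that month with the vaccination date and so discards recorded information. With one dose, items 3 and 4 give the same date, and the distinction between them has no effect.

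The consequence is that a partly dated event from a later month is shown as starting on the day of vaccination. In a first-in-human study, the Days 1-8 columns are where a reader looks for a close temporal link to the vaccine. A link would appear there that the recorded month rules out. SAEs are the most exposed because they are collected for six months.

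The SAE listing in SAP section 9.5 reports "number of days post dose and number of days post dose it became serious", as well as duration. The SAP does not say whether listings use recorded or imputed dates. If imputed dates are used, those entries carry the same error.

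**Working it through.** **Inputs.** One dose per participant (SAP 4.1). Study day = date − vaccination date + 1 (SAP 3.3). Time columns Days 1-8 and Days > 8 (SAP 9.4.3). Unsolicited AEs collected for 28 days and SAEs for 180 days (SAP 4.5.1). The plan states no figure for the effect of this rule, so there is none to reproduce.

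**Step 1: the rule.** Imputed study day = (vaccination date − vaccination date) + 1 = 1, whatever month is recorded. The event always goes to Days 1-8.

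**Step 2: an example (assumed dates).** Vaccination 20 March, onset recorded as July with no day. From 20 March to 1 July is 11 + 30 + 31 + 30 + 1 = 103 days, so 1 July is Day 104. Every possible true date is Day 104 or later; the rule gives Day 1.

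**Step 3: how often the month contradicts the rule.** Take every vaccination date in a 365-day year (2017) and every true onset day in a range, weighted equally. Keep month and year and delete the day. Compare the current rule with the alternative:

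imputed date = max(vaccination date, first day of recorded month)

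| Given that only the day is missing | Onset Days 9-29 | Onset Days 30-180 |
|---|---|---|
| Recorded month is later than the vaccination month, so Day 1 is impossible | 59.2% | 99.95% |
| Recorded month alone proves onset after Day 8 | 36.2% | 99.1% |
| Placed in Days 1-8, current rule | 100% | 100% |
| Placed in Days 1-8, alternative | 63.8% | 0.9% |
| Mean dating error, current rule | 18.0 days | 104.0 days |
| Mean dating error, alternative | 11.8 days | 14.7 days |

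Using 2016 vaccination dates changes these only trivially (59.0% in place of 59.2%, for example). The alternative is never later than the true onset, so it cannot move a true Day 1-8 event out of that column.

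**Step 4: the 28-day rows, a conditional effect.** Protocol 7.3.1 puts a 28-day window on the unsolicited AE endpoints. SAP 9.4.1 gives no window for those rows and includes SAEs, so as worded a late SAE is counted whatever its date. Only if the window is programmed as a date filter does the rule also matter here. It then brings every partly dated SAE from Days 30-180 inside the window. The alternative leaves 26.3% of those from Days 30-85 inside and none from Days 86-180. One such SAE, in a participant with no other event in the row, moves an arm from 0/20 (Clopper-Pearson 95% CI 0 to 16.8%) to 1/20 (0.1 to 24.9%).

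**The case against.** **The wording could mean something else.** The pronoun in the rule might refer only to the missing day, so that 20 March with onset July becomes 20 July (Day 123). That reading would give protocol items 3 and 4 different jobs. But both documents name the date of the last dose, not its day of the month, and first-dose and last-dose template language explains the redundancy equally well. The possible misreading is one more reason to reword the rule.

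**The lead-in is conditional.** It refers to missing data for a secondary endpoint, and its sense is unclear. On no reading does it restrict the rule by recorded month.

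**The direction is protective.** Neighbouring rules set missing severity to Grade 3 and missing relationship to related, and dating to vaccination overstates a temporal link rather than hiding one. That is fair, although neither document gives it as the reason. A worst-case value makes sense when timing is unknown, but not when the record excludes it. The alternative stays protective by taking the earliest date that the record allows.

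**Few events are at risk.** This stands. The largest errors apply to onsets after Day 29, when only SAEs are collected. Protocol section 13.2 cites a 1.0% SAE rate for the comparator. If that held in all arms, 60 × 0.01 = 0.6 SAEs would be expected, with a 0.99^60 = 55% chance of none, before requiring a late onset and a missing day. SAE follow-up, source verification and data cleaning before lock reduce the number further. For Days 9-29 the gain is partial: 64% of partly dated events would still be placed in Days 1-8.

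**Conclusion.** The rule is wrong as written, and the problem is minor. Whenever a month later than the vaccination month is recorded, Day 1 contradicts the data. Where that month begins after Day 8, the time column is certainly wrong too.

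The shares rest on uniform vaccination and onset dates and are conditional on only the day being missing. The documents give no frequency for such records, and the count may be zero. The Days 1-8 misplacement follows from the text; the effects on the SAE listing and the 28-day rows depend on programming choices the SAP leaves open.

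The six-month SAE row of Table 14.3.1.1 and the primary safety hypothesis in protocol section 7.1 do not depend on the imputed date. Non-serious AEs collected within 28 days stay in the 28-day counts either way.

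**What to change.** In SAP section 6.5, replace the start-date rule with two sentences:

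- If only the day is missing, impute the later of the vaccination date and the first day of the recorded month.
- If the month is also missing, impute the vaccination date.

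The second sentence is needed only because the first narrows the rule; the current SAP wording already yields that date. Also state whether listings show recorded or imputed dates.

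The cost is this wording, one programming rule and a matching edit to protocol section 7.5.2 item 3 at the next amendment. No new data are needed.

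A separate point, which matters even with complete dates, is to align SAP section 9.4.1 with protocol section 7.3.1 and footnote 3 of Table 14.3.1.1. Label the unsolicited AE rows as onset within 28 days and show later SAEs only in the six-month SAE row. That is a row label and a footnote, and the imputation fix does not depend on it.

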#### 6.6 Interim Analyses and Data Monitoring

Extensive safety monitoring will be provided for this protocol. The principal investigator (PI) and/or designated site staff will be responsible for continuous close safety monitoring of all study participants and for alerting the Sponsor if unexpected concerns arise or pause criteria are met.

To facilitate the planning of follow-up trials, analysis of unblinded primary safety data up to Visit 4 (Day 29), by treatment group, will be made available to the Sponsor after all participants have completed this visit and their data have been cleaned and verified. Immunogenicity data for the first 30 recruited participants are expected to be available at the same time and will be part of this analysis. Should recruitment be delayed, this interim analysis will proceed with safety data for available participants up to Day 29 as soon as the immunogenicity data for the first 30 participants becomes available.

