#### **SAFETY MONITORING:**

A Safety Review Committee (SRC) comprised of the Principal Investigator (PI), a medical expert with experience in vaccine pharmacovigilance not involved with the study, the Emmes medical monitor, Sponsor medical officer and SIIPL medical expert will be established to monitor participant safety throughout the duration of the study. The Emmes study statistician, with assistance of the data management staff, will prepare safety reports as needed for SRC discussions.

During the vaccination period, the SRC will review weekly the safety data. At any time during the study, the Emmes Coordinating Center will notify the SRC of ad hoc review if pause criteria may have been met.

The SRC reviews will be summarized with consensus recommendations to the study Sponsor as to whether there are safety concerns and whether the study should continue without change, be modified, paused or stopped. The SRC may request review of unblinded safety data by the vaccine pharmacovigilance expert in its deliberation. SRC consensus recommendations regarding modifying or stopping further enrolment may involve Sponsor consultation with the local regulatory authorities.

If at any time, a decision is made to discontinue administration of study product to all volunteers, expeditious notification will be provided by the sponsor to the US Food and Drug Administration (FDA), and by the PI to the University of Maryland, Baltimore (UMB) Institutional Review Board (IRB).

The following study pause rules will automatically pause or halt further vaccinations. However, volunteers already enrolled will continued to be followed for safety during the pause. These pause rules refer to suspected adverse reactions and will be triggered automatically if any of the event described below are met during the conduct of the study:

- One or more participants experience a serious adverse reaction.
- One or more participants experience a grade four injection site reaction.
- Two or more participants experience the same grade three injection site reaction.
- Two or more participants with the same severe (grade three) systemic reactogenicity signs or symptoms, within seven days following injection.
- Two or more participants experience the same vaccine-related grade three or higher clinical (including fever) or laboratory abnormality.

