#### **Analysis of Primary Safety Objective**

The primary aim of the study is to assess the safety of the study vaccine. All safety data (solicited local and systemic reactions and unsolicited AEs and SAEs) collected after participants are exposed to the study product will be included in the primary analysis of safety.

To assess safety, the number and percentage of participants experiencing at least one AE, and the number and percentage of participants experiencing each specific AE, categorized by body system and preferred term, will be tabulated by product received along with their corresponding two-sided exact 95% confidence intervals.

Fisher's exact test will be used to compare the proportion of participants with solicited local and systemic reactogenicity events between the MCV-5 group and the Menactra® Group. The primary purpose of statistical comparisons is to screen out potential solicited reactogenicity events that need further clinical evaluation. Therefore, they are not considered formal statistical hypothesis tests and it is acknowledged that there will be inflated Type I errors (i.e. inflated false statistical significances) from performing multiple unadjusted comparisons.

Changes in clinical laboratory values from baseline to end of treatment/follow-up will be analyzed descriptively.

To facilitate the planning of the follow-up trial, analysis of unblinded primary safety data up to Visit 4 (Day 29) by treatment groups will be made available to the Sponsor after all participants have completed this visit and their data have been cleaned and verified.

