## **Appendices:**

Appendix I Unblinded TableShells for Interim Safety Analysis

## **List of Abbreviations**

AE	Adverse Event
ALT	Alanine Aminotransferase
Alum	Aluminum phosphate
CDC	Centers for Disease Control
CI	Confidence interval
cm	Centimeter
CMV	conjugated meningococcal vaccines
CPCSEA	Committee for the Purpose of Control and Supervision of Experiments on Animals
CRF	Case report form
CRM	cross reactive material
CSR	Clinical Study Report
CVD	Center for Vaccine Development
EDC	Electronic data capture
ELISA	Enzyme linked immunosorbent assay
FA	Full Analysis
FDA	Food and Drug Administration
FIH	First in human
GMT	Geometric Mean Titer
HBV	Hepatitis B virus
HCG	human chorionic gonadotropin
HCV	Hepatitis C virus
HgB	Hemoglobin
HIV	Human immunodeficiency virus
ICD	Informed consent document
ICH	International Conference on Harmonisation of Technical Requirements for Registration of Pharmaceuticals for Human Use
Ig	Immunoglobulin
IM	Intramuscular
IUD	Intrauterine device
MedDRA®	Medical Dictionary for Regulatory Activities
N	Number (typically refers to participants)
PCR	Polymerase chain reaction

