#### **6.2** Timing of Analyses

Analysis of all available safety data up to Day 29 post-vaccination for all 60 participants and all immunogenicity data for the first 30 participants will be performed as soon as the immunogenicity data become available (see Section 6.6). The final analysis will be performed after the completion of the study. Extensive safety monitoring will be ongoing throughout the study.

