#### **6.6.1** Safety Review Committee

A Safety Review Committee (SRC), comprised of the PI, a medical expert with experience in vaccine pharmacovigilance not involved with the study, the Emmes medical monitor, SIIPL and PATH medical officer will monitor safety throughout the duration of the study. The Emmes study statistician with assistance of the data management staff will prepare safety reports as needed for SRC discussions. During the vaccination period, the SRC will review weekly safety data. At any time during the study, the Emmes Coordinating Center will notify the SRC of ad hoc review if pause criteria may have been met. The SRC reviews will be summarized with consensus recommendations to the study Sponsor as to whether there are safety concerns and whether the study should continue without change, be modified, or be stopped. The SRC may request review of unblinded safety data by the pharmacovigilance expert in its deliberation. SRC consensus recommendations regarding modifying or stopping further enrolment may involve Sponsor consultation with the local regulatory authority.

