## 12 SUMMARY OF CHANGES IN CONDUCT OF THE STUDY OR PLANNED ANALYSES

#### 13 REFERENCES

#### 14 TABLES, FIGURES, AND LISTINGS

#### **GENERAL ASSUMPTIONS:**

#### Implementation Notes:

- All figures presented are sample figures and do not include real study data.
- The number of participants presented are not real study data, but generic examples of how to present the data for the different treatment groups. The number of participants will be dependent upon the data observed in the study.
- The total number of participants for each treatment group are not actual numbers, but generic
  examples of how to present the data for the different treatment groups. The total number of
  participants will be dependent upon the data observed in the study.

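### If recruitment is delayed, SAP 6.6 lets the unblinded by-arm interim reach the Sponsor before all participants complete Day 29, contrary to Protocol 7.5.2 and SAP 6.2; the SAP also adds first-30 immunogenicity that the protocol's interim does not include

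*SAP*

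**What the plan says.** Protocol 7.5.2, under the analysis of the primary safety objective, provides for one unblinded release before the end of the study. It covers primary safety data to Visit 4 (Day 29), which "by treatment groups will be made available to the Sponsor after all participants have completed this visit and their data have been cleaned" and verified. The stated purpose is to help plan the follow-up trial. Immunogenicity is not mentioned there.

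SAP 6.6 repeats that rule and then makes two additions:

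- **Content:** "Immunogenicity data for the first 30 recruited participants are expected to be available at the same time and will be part of this analysis".
- **Timing:** "Should recruitment be delayed, this interim analysis will proceed with safety data for available participants up to Day 29", as soon as the first-30 titers are in. The sentence does not define a delay and does not repeat the cleaning and verification requirement.

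SAP 6.2 describes the same interim as safety to Day 29 for all 60 participants, and says that this together with "all immunogenicity data for the first 30 participants will be performed as soon as the immunogenicity data become available (see Section 6.6").

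Three further provisions bear on the consequences. The Safety Review Committee (SRC) includes the Sponsor's medical officer; the Protocol synopsis says that the PI, an outside expert, the medical monitor, "Sponsor medical officer and SIIPL medical expert will be established to monitor participant safety throughout the duration of the study". The committee's stated route to unblinded data is narrow: "The SRC may request review of unblinded safety data by the pharmacovigilance expert in its deliberation". Under Protocol 9.2.1, the Sponsor restarts the study after the committee's review and recommendation.

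**The concern.** The protocol's rule does useful work. When by-arm tables leave the data centre, every vaccination has been given and every Day 29 visit is over, so knowledge of the arms cannot affect enrolment, vaccination or the 28-day adverse event period. The SAP's delay sentence removes that protection in the situation where recruitment is still open.

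In that situation someone at the Sponsor could hold arm-level safety and titer results while also taking part in a recommendation to continue, modify or stop, or in a decision to restart after a pause. Neither document limits who at the Sponsor receives the release. The expert-only route to unblinded data suggests that committee members were not meant to work from arm-level tables.

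The second issue is one of authority. A SAP may add detail to a protocol, but dropping a condition on unblinding and adding an unblinded look at a secondary endpoint go beyond detail.

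**Working it through.** **The texts side by side**

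| | Protocol 7.5.2 | SAP 6.2 | SAP 6.6 default | SAP 6.6 if delayed |
|---|---|---|---|---|
| Safety set | all participants to Day 29 | all 60 to Day 29 | all participants to Day 29 | whoever is available |
| Trigger | last Visit 4, data clean | first-30 titers | last Visit 4, data clean | first-30 titers |
| Immunogenicity | none mentioned | first 30 | first 30 | first 30 |

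The delayed column conflicts with the protocol on safety set, trigger and content. It also conflicts with SAP 6.2: if the titers arrive before the last Day 29 visit, an analysis cannot both start on the titers and cover all 60.

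**The plan's own precision figures (Protocol 7.4, 20 per arm)**

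- Chance of at least one event at an 11% rate: 1 − 0.89^20 = 90.3% (plan: above 90%).
- One-sided 95% upper bound with no events: 1 − 0.05^(1/20) = 13.9% (plan: about 14%).

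Both reproduce.

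**How many would have Day 29 data at an early release**

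The documents give neither a recruitment rate nor an assay time, so both are assumptions. Let r be enrolment per week after participant 30 and T the weeks from that participant's Day 29 sample to available titers. Vaccination to sample is 4 weeks.

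- With Day 29 data at release: min(60, 30 + rT).
- Not yet vaccinated at release: max(0, 30 − r(4 + T)).

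Each cell gives participants with Day 29 data / participants not yet vaccinated:

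| r per week | T = 4 | T = 8 | T = 12 |
|---|---|---|---|
| 1 | 34 / 22 | 38 / 18 | 42 / 14 |
| 2 | 38 / 14 | 46 / 6 | 54 / 0 |
| 3 | 42 / 6 | 54 / 0 | 60 / 0 |
| 4 | 46 / 0 | 60 / 0 | 60 / 0 |

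Someone is still unvaccinated only if r is below 30/(4 + T), which is 3.75, 2.50 or 1.88 per week for T = 4, 8 or 12. If participant 30 uses the full 14-day visit window (Protocol 5.2.6), the divisor becomes 6 + T and the thresholds fall to 3.00, 2.14 and 1.67. Where nobody is unvaccinated, some may still be inside the 28-day period: at r = 4 and T = 4, 60 − 46 = 14 have not reached Day 29.

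**Interim safety precision over that range**

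| Participants (about per arm) | Rate ruled out by zero events | Chance of seeing an 11% event |
|---|---|---|
| 34 (11) | 23.8% | 72.2% |
| 46 (15) | 18.1% | 82.6% |
| 60 (20) | 13.9% | 90.3% |

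**Interim immunogenicity precision**

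If the first 30 recruited are the first 30 randomized, five blocks of six (Protocol 2.4.7) give 10 per arm. The exact 95% interval for 10/10 responders is 69.2% to 100%, against 83.2% to 100% for 20/20. For 8/10 it is 44.4% to 97.5%, against 56.3% to 94.3% for 16/20.

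All of these figures describe how much the interim could show. They do not measure bias from early unblinding, which the documents give no means to quantify.

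**The case against.** The best defence is that the departure is conditional and its consequences small. Most of this stands:

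- SAP 6.6 follows the protocol by default. A reader might infer that the SAP simply replaces the protocol's rule; it does so only if recruitment is delayed.
- Participants and site safety assessors stay blinded throughout, and the pause rules (Protocol 9.2, SAP 6.6.2) trigger automatically on counts that do not refer to arm. Only discretionary judgement is exposed.
- The blind is not absolute under the protocol either. Protocol 8.8.2 unblinds IND Safety Reports on serious unexpected suspected reactions, with copies to the PI and the committee. That is case-level information, however, not by-arm tables.
- No formal hypothesis testing is planned (Protocol 7.4) and the final analysis keeps all 60. A reader might infer inflated type I error or a compromised final analysis; the documents support neither.
- Interim safety precision need not suffer. Ten per arm (zero events rules out 25.9%) is only a limiting case, and several assumed combinations give all 60.

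A reader might also infer concealment, because the SAP section headed "SUMMARY OF CHANGES IN CONDUCT OF THE STUDY OR PLANNED ANALYSES" has no entry and the appendix is listed as "Appendix I Unblinded TableShells for Interim Safety Analysis". This is weak support. The SAP's References section is equally empty, which fits an unfilled template or text lost in extraction, and the appendix itself is not in the supplied text.

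Finally, one might blame the delay sentence for uncertainty over when the blind is broken for setting the per-protocol exclusions. That question arises equally under the protocol's own release, which is also by arm and precedes the final database lock (Protocol 10.3).

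None of this reconciles the release rules or gives the first-30 immunogenicity a place in the protocol.

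**Conclusion.** The inconsistency is certain on the text. In the delayed case, SAP 6.6 contradicts Protocol 7.5.2 and SAP 6.2 on when by-arm results may be released and on whom. SAP 6.2 and 6.6 also add an unblinded immunogenicity look that the protocol's interim does not mention.

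The practical impact is limited and conditional. It requires a delay, which is undefined, and a recruitment rate slow enough that vaccination or 28-day follow-up is still open when the titers arrive. Under the assumed 1 to 4 per week and 4 to 12 weeks of assay time, 34 to 60 participants (about 11 to 20 per arm) would have Day 29 data, and between 22 and none would still be unvaccinated. What is exposed is the discretionary judgement of the Sponsor and its committee member on continuing or restarting. The final analysis and any error rate are not affected. The point should still be corrected, because two documents governing a double-blind trial state different unblinding rules.

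**What to change.** **Preferred.** Delete the SAP 6.6 sentence on delayed recruitment and change the trigger in SAP 6.2 to match, so that the by-arm release follows Protocol 7.5.2. If first-30 immunogenicity is wanted, release it only at that same time, add it to the protocol, and check that SAP Appendix I has shells for it.

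**If the early look is kept.** Amend the protocol to allow it, define delay, state whether cleaning and verification still apply, reconcile SAP 6.2 with 6.6, and record the change in SAP Section 12. Restrict recipients to named functions at the Sponsor that are not on the SRC and take no part in decisions to continue or restart.

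**Separately, under either option.** Finalise the SAP and the per-protocol exclusion criteria before this by-arm release, since Protocol 7.1 and 7.5.1 and SAP 6.3.3 require both to be settled before unblinding.

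**Cost.** Removing the sentence and the interim immunogenicity needs only SAP wording. Keeping either needs a protocol amendment with IRB review (Protocol 12). Planning of the follow-up trial may have to wait for the last Day 29 visit, which Protocol 7.5.2 already accepts. Protocol 2.3 takes both formulations into Phase 2 and leaves the choice between them to that trial, so this interim need not make it.
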